4.1. Inclusion Criteria

All responses must be “yes” to include a subject in the study:

1. ≥ 18 years old.
2. Medical record documentation of recurrent CDI per the study definition, that includes either: a) at least one recurrence after a primary episode and has completed at least one round of standard-of-care oral antibiotic therapy or b) has had at least two episodes of severe CDI resulting in hospitalization within the last year.
3. A positive stool test for the presence of toxigenic *C. difficile* within 30 days prior to enrollment.
4. Is currently taking or was just prescribed antibiotics to control CDI related diarrhea at the time of enrollment.
Note: Subject's CDI diarrhea must be controlled (<3 unformed/loose, i.e. Bristol Stool Scale type 6-7, stools/day for 2 consecutive days) while taking antibiotics during screening
5. Willing and able to have an enema(s).
6. Willing and able to complete the stool and serum testing required for the study.
7. Agrees not to take non-dietary probiotics through 8 weeks after receiving the last study enema (including OTC and prescription).
8. Agrees not to take any oral vancomycin, metronidazole, fidaxomicin, rifaximin, nitazoxanide and IVIG through the 8-week follow-up assessment unless newly prescribed by a treating investigator during the course of the study as a result of recurrent CDI diagnosis.
9. Agrees to practice a form of effective contraception during study participation, does not apply to persons with documented non-child bearing potential.
10. Has a negative urine pregnancy test at the time of enrollment and on the day of each enema prior to administration (persons of child-bearing potential only).
11. Willing and able to provide informed consent and local privacy authorization as applicable.
12. Willing and able to complete the required Subject Diary.
13. Willing and able to meet all study requirements, including attending all assessment visits and telephone calls.

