4.2. Exclusion Criteria

All responses must be “no” to include a subject in the study:

1. A known history of refractory CDI.
2. Currently has continued CDI diarrhea despite being on a course of antibiotics prescribed for CDI treatment.
3. Requires antibiotic therapy for a condition other than CDI.
4. Previous fecal transplant, RBX2660 treatment, receipt of CDI vaccine or treatment with CDI monoclonal antibodies prior to study enrollment.

5. History of inflammatory bowel disease (IBD), e.g., ulcerative colitis, Crohn's disease, or microscopic colitis.
6. Diagnosis of irritable bowel syndrome (IBS) as determined by Rome III criteria.
7. History of chronic diarrhea.
8. History of celiac disease.
9. Disease symptoms (diarrhea) caused by a confirmed intestinal pathogen other than *C. difficile*.
10. Currently has a colostomy.
11. Intraabdominal surgery within the last 60 days.
12. Evidence of active, severe colitis.
13. History of short gut syndrome or motility disorders.
14. Requires the regular use of medications to manage bowel hypermotility.
15. Planned therapy in the next 3 months that may cause diarrhea (e.g., chemotherapy).
16. Planned surgery requiring perioperative antibiotics within 6 months of study enrollment.
17. Life expectancy of < 6 months.
18. Compromised immune system (e.g., HIV infection with CD4 count <200/mm³; inherited/primary immune disorders; immunodeficient or immunosuppressed due to a medical condition or medication).
Note: Eligible HIV patients who have a CD4 count >200/mm³ who are on stable, highly active anti-retroviral therapy may be considered for enrollment.
19. Taking systemic steroids > 20 mg prednisone a day or prednisone-equivalent, or is expected to be on steroids (> 20 mg prednisone a day or equivalent) after enrollment through 8 weeks after completing the assigned study treatment.
Note: Eligible patients taking a steroid dose equivalent to prednisone 20 mg/day for >2 weeks, antimetabolites (e.g., azathioprine, 6-mercaptopurine, or low-dose methotrexate for autoimmune disease), calcineurin inhibitors (e.g., tacrolimus and cyclosporine), or mycophenolate mofetil may be enrolled only after consultation with the Medical Monitor, and only if the doses have been stable (except for drug therapeutic monitoring adjustments for calcineurin inhibitors) for 90 days and have not been associated with diarrhea prior to the current episode of CDI.
20. An absolute neutrophil count of <1000 cells/µL during screening.

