6.6. Randomization

Once enrolled (informed consent obtained), in order to be randomized and treated:

1. Subject must meet all of the inclusion and none of the exclusion criteria;
2. Antibiotics will have been administered for a minimum of 10 consecutive days prior to the washout period;
3. CDI symptoms must be under control leading into the antibiotic washout period.

After enrollment and confirmation of inclusion/exclusion criteria compliance, including criteria confirmed by central laboratory testing, the study coordinator or other trained and authorized site staff randomize the subject in the Interactive Response Technology (IRT) System and ensures study treatment is completed within 4-14 calendar days of randomization. Ultimately, the study treatment needs to be administered within 21 days of the Screening visit.

The randomization schedule will be created using randomized blocks within four strata based on antibiotics used at screening (Vancomycin alone, Vancomycin in combination, Fidaxomicin or Other), and randomized subjects will be assigned one of two treatments (Group A or Group B) within the appropriate stratum. The randomization will not be stratified by site, so each site will draw from the same set of blocks. A subject will be assigned the next available treatment allocation from the randomization list. The randomization code and the date and time of randomization will be captured in the IRT.

Enrolled (consented) subjects who are randomized but exited prior to attempting the blinded treatment may be re-enrolled if another CDI recurrence occurs and thus randomized under a different subject identification numbers (re-randomized). If this occurs, they will be included in the analysis using their second randomization assignment and subsequent assessments and will only be counted once towards the total randomized.

Treatment will be assigned in the following proportions: 2:1 to yield a total of up to 270 randomized and treated subjects, or approximately 180 subjects randomized to treatment with RBX2660 and 90 subjects randomized to Placebo. Subjects who are randomized but exit prior to the administration of the first blinded enema may be replaced with additional subjects which could cause overall number of subjects randomized to be greater than the 270 anticipated, however no more than 270 subjects will be treated with

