7.6.3 Other Endpoint Analysis

An initial assessment will be completed during the primary efficacy analysis as follow-up data allows with a complete analysis to be provided with the full study results for applicable other analyses. Additionally, the other analyses will be conducted on other efficacy populations as needed.

7.6.3.1 Comparison of baseline characteristics in subjects successful with one dose of RBX2660 vs. those who were unsuccessful.

A multivariate analysis or regression analysis will be used to identify predictors (if any) for subject success with one RBX2660 dose vs. those who were unsuccessful.

7.6.3.2 Cdiff32 scores at Screening, 1-week, 4-week, and 8-week assessment visits, and 3 and 6 month phone assessments.

Changes from Screening in the Cdiff32 scores will be summarized using descriptive statistics by treatment arm. Last observation carried forward (LOCF) will be used to impute missing post-baseline data. No inferential statistics will be performed.

7.6.3.3 Subject fecal microbial composition at Screening, and 4 and 8- weeks and 3 and 6 months after blinded study treatment.

Descriptive statistics will be used to present the changes from Screening fecal microbial composition to those at 4 weeks, 8 weeks, 3 months and 6 months after blinded study treatment for those subjects treated with RBX2660 and those receiving Placebo.

7.6.3.4 Charlson Comorbidity Index at Screening, 8 week visit, and 3-, 6- month phone assessments.

A comorbidity index score will be documented for all subjects at Screening and compared to subsequent scores at 8 weeks, 3 months and 6 months. An initial assessment will be completed during the primary efficacy analysis as follow-up data allows with a complete analysis to be provided with the full study results. Additional analysis may be done of Placebo subjects who

were documented treatment failures after blinded treatment then treatment successes following unblinded RBX2660 treatment.

7.6.3.5 Atlas score for CDI severity of qualifying CDI.

Quantification of CDI severity scores for subjects at the time of the CDI recurrence that qualified them for enrollment into the study based on the ATLAS Scoring System. Data from the qualifying CDI event will be used (see table below), including the protocol required eligibility criteria of treatment with systemic antibiotics prior to randomization. However, if data points are not available, baseline data may be substituted.

Parameter	0 Points	1 Point	2 Points

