Age (years)	< 60	60 – 79	≥ 80
Temperature (°C)	≤ 37.5	37.6 – 38.5	≥ 38.6
Leukocyte count (total)/mm ³	< 16,000	16,000 – 25,000	> 25,000
Albumin (g/L)	> 35	26 – 35	≤ 25
Systemic concomitant antibiotics during CDI RX	No	-	Yes

7.6.3.6 Recurrence of CDI within 8 weeks in Placebo subjects who were documented study treatment failures and then received RBX2660 through open-label.

Treatment success for documented Placebo failures after receiving RBX2660 will be completed using a Chi-square test comparing the treatment success of blinded placebo subjects as compared to the success of placebo subjects who received RBX2660. This analysis will be completed with the full study results rather than the primary efficacy analysis as it requires data on the outcome following any unblinded RBX2660 enemas received.

7.6.3.7 Recurrence of CDI within 8 weeks of unblinded (open-label) RBX2660 treatment in subjects who received a blinded dose of RBX2660.

Determine the treatment success rate of those subjects randomized to RBX2660 who were deemed an initial treatment failure then went on to receive an unblinded RBX2660 enema (two RBX2660 enemas). This success rate will be calculated at 8 weeks following the second

RBX2660 enema and compared to the blinded success rate of the RBX2660 arm using a Chi-square test.

7.6.3.8 Occurrence of CDI through 6 months in all subjects receiving a single dose of RBX2660.

Determine the combined treatment efficacy for RBX2660 randomized subjects plus Placebo randomized subjects who were documented failures after blinded treatment then received a unblinded RBX2660 enema. This analysis will be completed with the full study results rather than the primary efficacy analysis as it requires data on the outcome following any unblinded RBX2660 enemas received. Both treatment success and treatment durability will be analyzed;

- Treatment success rate for the prevention of CDI recurrence
- Treatment success rate for the prevention of new CDI episodes (those with onset occurring beyond 8 weeks after study treatment)

7.6.3.9 Concentration of vancomycin resistant enterococcus in stool samples for subjects who were carriers at baseline.

Lab generated values for the presence of vancomycin resistant enterococcus based on submitted stool samples at baseline and at 1-, 4-, 8-weeks, and 3 and 6 months will be assessed for all subjects to identify any trends in the clearance of vancomycin resistant enterococcus following enema treatment.

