8.8 Examination of Subgroups

Subgroup analysis of age (< 65 years, ≥ 65 years), sex (Female, Male), race group (White, Non-white), ethnicity (Hispanic-Latino, not Hispanic-Latino), site geography (outside the US, Eastern

US*, Southern US*, Northern US*, Western US*) and number of previous episodes of CDI recurrence at baseline will be conducted on the primary efficacy analysis if a sufficient sample size exists for each subgroup. The primary efficacy analysis will also be conducted based on vancomycin use for the qualifying CDI episode \leq 14 days and $>$ 14 days using subjects who were stratified based on Vancomycin Alone. These analyses will include all analysis populations (mITT and PP) to understand any differences.

*States included in the identified US geographical regions are as follows:

- Eastern US: Connecticut, Delaware, District of Columbia, Maine, Maryland, Massachusetts, New Hampshire, New Jersey, New York, Ohio, Pennsylvania, Rhode Island, Vermont, Virginia, West Virginia
- Southern US: Alabama, Arkansas, Georgia, Florida, Kansas, Kentucky, Louisiana, Mississippi, North Carolina, Oklahoma, South Carolina, Tennessee, Texas
- Northern US: Illinois, Indiana, Iowa, Michigan, Minnesota, Missouri, Nebraska, North Dakota, South Dakota, Wisconsin
- Western US: Arizona, California, Colorado, Idaho, Montana, Nevada, New Mexico, Oregon, Utah, Washington, Wyoming

Other sub-groups may be considered if there are enough subjects in each group such as; qualifying CDI event treated as inpatient vs. outpatient, the severity of the qualifying event based on the ATLAS scores, treatment length or type of antibiotics taken at the time of the CDI qualifying event, and others yet undetermined.

Cochran-Mantel-Haenszel tests will be used to assess homogeneity of the odds ratios in the subgroups.

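### SAP 7.6.3.5 counts the CDI treatment itself as a concomitant antibiotic, so on its natural reading every subject gets 2 ATLAS points, and unflagged baseline values may stand in for missing event values

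*SAP*

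**What the plan says.** SAP 7.6.3.5 sets the target of the score: "Quantification of CDI severity scores for subjects at the time of the CDI recurrence that qualified them for enrollment". It draws on data from the qualifying event, "including the protocol required eligibility criteria of treatment with systemic antibiotics prior to randomization". The next sentence adds: "However, if data points are not available, baseline data may be substituted".

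The scoring table that follows has five rows. Age, temperature, leukocyte count and albumin each score 0, 1 or 2. The fifth row, "Systemic concomitant antibiotics during CDI RX", scores 0 for No and 2 for Yes, with no 1-point level.

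The protocol describes the required antibiotic in two places. Inclusion criterion 4 (Protocol 4.1) reads "Is currently taking or was just prescribed antibiotics to control CDI related diarrhea at the time of enrollment". Protocol 6.6 adds: "Antibiotics will have been administered for a minimum of 10 consecutive days prior to the washout period". Exclusion criterion 3 (Protocol 4.2) removes anyone who "Requires antibiotic therapy for a condition other than CDI".

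ATLAS is listed among the other efficacy endpoints (Protocol 2.7, SAP 6.4.3) and is a per-subject baseline descriptor (SAP 7.3). SAP 8.8 names it as a possible subgroup factor: "the severity of the qualifying event based on the ATLAS scores".

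**The concern.** The text and the table do not fit together. The table row asks about an antibiotic that accompanies CDI treatment. The text puts into the score the antibiotic that every subject must have taken to enter, and that antibiotic is the CDI treatment. An item meant to distinguish subjects then becomes a constant, and the severity reported for the trial population is too high on an absolute scale.

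The substitution rule raises a second problem. A baseline value may have been taken after CDI treatment began, so a score that contains one may describe a partly or fully treated state. The SAP does not limit how many items may be substituted, does not flag the scores affected and plans no sensitivity analysis.

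What is at stake is the description of disease severity at entry, any fixed ATLAS cut-off, and any subgroup formed from the score. If event values are missing unevenly, such a subgroup would partly sort subjects by data availability.

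**Working it through.** The plan states no ATLAS figure to reproduce, so the check is of the scoring rule itself.

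**Antibiotic item**

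Inputs, from the SAP 7.6.3.5 table: four items scored 0/1/2 and one item scored 0/2.

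- Four items without the antibiotic row: 4 × 0 to 4 × 2 = 0 to 8.
- Table as labelled: 0 + 0 to 8 + 2 = 0 to 10.
- Text as naturally read, item Yes for all: 0 + 2 to 8 + 2 = 2 to 10. Only the four other items (0 to 8) still discriminate.

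Let q be the share of subjects truly on a non-CDI systemic antibiotic during the qualifying episode. The item's mean should be 2q and the rule makes it 2, so the mean overstatement is 2 − 2q = 2 × (1 − q). The documents do not give q. Over an assumed range:

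| q (assumed) | Overstatement, points |
|---|---|
| 0% | 2 × 1.0 = 2.0 |
| 10% | 2 × 0.9 = 1.8 |
| 30% | 2 × 0.7 = 1.4 |

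Both arms receive the same constant. With equal q in the two arms, as randomization gives in expectation, the between-arm difference in mean score does not change.

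**Baseline substitution**

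Where the substitute values come from:

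- SAP 7.3 defines baseline as within 30 days before, or on, the enema day.
- Albumin is part of the metabolic panel, which is drawn at screening (Protocol 6.5) and not on the enema day (Protocol 6.7).
- Blood count and temperature are taken at both visits.
- Enema-day values follow at least 10 days of antibiotics, confirmed symptom control and a 24–72 hour washout (Protocol 6.6, 6.7).
- Screening values come from a subject already on CDI antibiotics or only just prescribed them (Protocol 4.1). They may therefore date from during treatment or lie close to the event.

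Illustration with assumed values: age 65 (1 point), 39.0 °C (2), leukocytes 20,000/mm³ (1), albumin 30 g/L (1), no non-CDI antibiotic.

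- Table as labelled, event values: 1 + 2 + 1 + 1 + 0 = 5.
- SAP antibiotic rule, event values: 1 + 2 + 1 + 1 + 2 = 7.
- SAP antibiotic rule, the three measured items replaced by normal baseline values: 1 + 0 + 0 + 0 + 2 = 3.

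In this example the same episode scores 7 or 3 under the SAP, depending on which data are on file. The two effects run in opposite directions here.

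**Consistency within the SAP**

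SAP 8.3 states that no imputation is used. It names two exceptions: last observation carried forward for Cdiff32 and the adjustments for adverse event data. The ATLAS substitution is neither.

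**The case against.** **The SAP never says to score Yes for everyone.** That is true; it is an inference. But the table has only one antibiotic row, so the phrase about required antibiotics has nowhere else to act. If something else was meant, the sentence is too unclear to score from and still needs rewriting.

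**A constant does little harm.** This largely stands. Adding 2 to every score leaves spread and between-arm comparison alone and can be subtracted. What changes is the absolute level, any fixed cut-off, and the ranking of any subjects who truly had another antibiotic.

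**Substitution is optional and may be close to the truth.** This stands in part. A just-prescribed subject's screening values can approximate the event, and symptom control is not a condition of the screening blood draw. Objective 6 (Protocol 2.3) also speaks of baseline severity, so a baseline fallback is not foreign to it. The endpoint and SAP 7.6.3.5, however, tie the score to the qualifying event, and an unflagged mixture of the two cannot be taken apart in the summary.

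**Stronger readings to avoid.** A reader might infer from exclusion criterion 3 that the corrected item would be 0 for nearly everyone. The documents do not show this: the criterion is judged at entry, and the qualifying stool test may be up to 30 days older, so a completed course for another condition is possible. A reader might also infer that substitution removes 6 points. That is only the arithmetic ceiling (3 items × 2), reached when all three event values are missing, would each have scored 2, and are replaced by values scoring 0. Nor does it follow that no interpretable severity figure remains, since the share of missing event values is not given.

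**Conclusion.** The point holds as a scoring fault of limited reach. On the natural reading of SAP 7.6.3.5, every subject receives 2 points for the CDI treatment, the scale becomes 2–10, and mean severity is overstated by 2.0 to 1.4 points for q between 0 and 30%. That range for q is an assumption. The meaning of the item is taken from the SAP's own row label, because the cited scoring paper was not available.

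The substitution rule is a separate weakness of unknown size. Its effect depends on how many event values are missing and on how long after the start of treatment the substitutes were taken.

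Neither fault touches the primary or secondary test. Both affect a descriptive other endpoint, a baseline characteristic and an optional subgroup. A change is worth making because the score would otherwise be reported as event severity when it is not cleanly that, and because SAP 7.6.3.5 and 8.3 disagree.

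**What to change.** In SAP 7.6.3.5:

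- Delete "including the protocol required eligibility criteria of treatment with systemic antibiotics prior to randomization".
- Score the antibiotic item Yes only for a systemic antibiotic other than the CDI treatment, taken during treatment of the qualifying episode, using the concomitant-medication and CDI-history data.
- The documents do not state that the indication for non-CDI drugs is recorded. If it cannot be established, report the four-item score (0–8) without this item.
- Report event-time scores with the number missing for each item. Keep baseline substitution only as a flagged score, reported separately.

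In SAP 8.8, base any ATLAS subgroup on the event-time score, with the substituted score as a sensitivity check. In SAP 8.3, list the substitution as an exception.

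The cost is SAP wording and some extra programming. The drawback is fewer complete event-time scores. Those that remain may over-represent sicker or hospitalized subjects, which is the reason to show the substituted version alongside rather than drop it.

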1.5.2. Phase 2B Study Protocol 2014-01 Interim Study Data

EFFICACY RESULTS: The efficacy objectives of the study were analyzed using the n=127 treated subjects (n=41 Group A, n=44 Group B, n=42 Group C) in the ITT population. In particular the assessment of RBX2660 as compared to placebo for subjects with a history of recurrent CDI and the assessment of further treatment on subjects who are confirmed treatment failures.

While the anticipated primary efficacy endpoint of two (2) enemas of RBX2660 administered 7 \pm 2 days apart (61.0%) as compared to placebo (45.5%) in the blinded phase was not met, the key secondary efficacy endpoint of one (1) enema of RBX2660 (66.7%) as compared to the placebo group (45.5%) was met with a p-value of 0.048. All other secondary objectives for the study were also met. The active RBX2660 treatment groups A and C in the were compared to each other with a p-value of 0.589 indicating no difference between one RBX2660 enema and two (2) administered 7 \pm 2 days apart. As such, an analysis using the combined RBX2660 treatment groups A and C with a success rate of 63.9% (53/83) was compared to the placebo (45.5%) also with a significant p-value of 0.046 by Pearson's chi-square.

Additionally, analysis of the ITT population was done to establish the overall efficacy rate for RBX2660 which took into consideration both blinded and open label treatments. The resulting overall efficacy for all subjects treated with RBX2660 (n=107) was 88.8% which compared to the placebo rate of 45.5% was also significant with a p-value of <0.0001.

Finally, an analysis of the ITT placebo group subjects using them as their own control by comparing blinded treatment success (placebo treatment) to open label success (after RBX2660 treatment) showed a significant increase in success rate from 45.5% (20/44) in the blinded phase to 87.5% (21/24) after treatment with RBX2660 with a resulting p-value of <0.0001.

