4.4 Determination of Sample Size

To demonstrate a 69% success with one dose of the RBX2660 treatment group vs. 47% success in the Placebo control group, 240 subjects are required (power > 90%, nominal 2.5% type I error rate). Up to an additional 30 subjects will be enrolled to allow for a 10% loss-to-follow up rate, for a total of approximately 270 subjects. Considering the 2:1 randomization, this results in approximately 180 subjects in the RBX2660 arm and 90 subjects in the Placebo arm. Enrolled subjects who have signed consent and withdraw for any reason prior to administration of the first blinded enema will be replaced without counting toward the sample size cap. Replacement subjects will be randomized to ensure proper blinding.

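### SAP 7.6.3.6 and 7.6.3.7 test open-label retreatment of failures against the whole blinded arm they came from; with no concurrent control and bias of unknown sign, the p-values cannot answer Other Objectives 7 and 8

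*SAP*

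**What the plan says.** SAP 7.6.3.6 takes documented placebo failures who then received open-label RBX2660 and applies a chi-square test "comparing the treatment success of blinded placebo subjects as compared to the success of placebo subjects who received RBX2660". SAP 7.6.3.7 takes RBX2660 failures given a second, unblinded enema. Their success rate at 8 weeks is to be "compared to the blinded success rate of the RBX2660 arm", again by chi-square.

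These analyses correspond to Other Objectives 7 and 8 (Protocol 2.3, SAP 3.3). SAP 8.1 sets a default of two-sided 0.05, and neither section limits how the result may be read. The closed testing procedure in SAP 8.7 covers only the primary and secondary endpoints, so both tests lie outside it.

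The way subjects reach the open-label enema is set out elsewhere:

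- Retreatment is optional for a failure and unblinded, and is given up to 21 days after failure is determined. A subject who is to have a non-study treatment is exited first (SAP 4.1).
- Before the blinded enema, at least 10 consecutive days of antibiotics are required (SAP 4.1). Before the open-label enema, antibiotics are left to the investigator (Protocol 3.8).
- No failure is retreated with placebo, and failures who are not retreated are not used as a comparator.

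**The concern.** A chi-square test of two proportions answers a question about treatment only if the groups would have had the same expected success without it. Here one group is selected from the other by its outcome, then narrowed by choice, treated openly and observed later. Equal success in the two groups is therefore not a hypothesis about RBX2660.

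For 7.6.3.7 the null is also the wrong one. A second enema could help failures considerably and still succeed less often than the first did in an unselected arm. A non-significant result would not show that the second enema fails, nor that it works as well as the first.

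What is at stake is interpretation. The programme has read such a contrast as evidence before: Protocol 1.5.2 treats 2014-01 placebo subjects as their own controls and reports a significant rise from "45.5% (20/44) in the blinded phase to 87.5% (21/24) after treatment with RBX2660". Protocol 1.6 describes the present study as confirming a strategy that includes a second enema on recurrence. A p-value from 7.6.3.7 is likely to be quoted for that purpose, and it cannot serve it.

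**Working it through.** **Inputs.** The two sections give no figures of their own. Design rates and arm sizes come from SAP 4.4: "To demonstrate a 69% success with one dose of the RBX2660 treatment group vs. 47% success in the Placebo control group", with "approximately 180 subjects in the RBX2660 arm and 90 subjects in the Placebo arm". The 2014-01 counts come from Protocol 1.5.2 and SAP Appendix Table 1. Full uptake of retreatment, between-subject correlation and non-drug shifts are assumptions, shown as ranges.

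**1. The plan's own sample size.** Placebo n = [1.96·√(1.5·p̄q̄) + 1.2816·√(p_C·q_C + p_T·q_T/2)]² / 0.22², with p̄ = (0.47 + 2×0.69)/3 = 0.617. This gives 77.1, so 78 placebo and 3×78 = 234 in total, close to the stated 240. The design rates are usable as inputs.

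**2. Group sizes.** Expected failures are 90×0.53 ≈ 48 on placebo and 180×0.31 ≈ 56 on RBX2660. With full uptake, 7.6.3.6 compares 48 subjects with the 90 that contain them, and 7.6.3.7 compares 56 with 180.

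**3. Does reusing subjects distort the test?** If every subject has the same success probability p and retreatment changes nothing, second-period success has mean p however many failed first, so the two proportions are uncorrelated. In 20,000 simulated trials per scenario, significance favouring retreatment occurred in 2.8% (7.6.3.6) and 2.6% (7.6.3.7), against a nominal 2.5%. Overlap alone does not inflate the error.

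**4. Selection on failure.** Let success probabilities vary between subjects with correlation ρ between a subject's two outcomes. Then P(fail, then succeed) = p(1−p)(1−ρ). Dividing by P(fail) = 1−p gives expected retreatment success p(1−ρ), with no real change in effect.

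| ρ | 7.6.3.6 (p = 47%) | 7.6.3.7 (p = 69%) |
|---|---|---|
| 0 | 47% | 69% |
| 0.1 | 42% | 62% |
| 0.2 | 38% | 55% |
| 0.3 | 33% | 48% |

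This selection works against retreatment. At ρ = 0.1 or more and no other shift, simulated significance in its favour falls below 1%.

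**5. A non-drug shift in the second period** (time, open-label care, who elects). At ρ = 0, a shift favouring retreatment produces significance in its favour this often:

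| Shift, points | 7.6.3.6 | 7.6.3.7 |
|---|---|---|
| +5 | 9.6% | 10% |
| +10 | 22% | 30% |
| +15 | 41% | 61% |
| +20 | 63% | 88% |

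**6. The two together.** A shift δ is cancelled when δ = ρp. At ρ = 0.2 that is 0.2×47 = 9.4 points for 7.6.3.6 and 0.2×69 = 13.8 points for 7.6.3.7. The net bias favours retreatment above these values and opposes it below them. The documents give no value for ρ or δ, so the sign is unknown.

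**7. The 2014-01 contrast** (Pearson chi-square, no continuity correction).

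- Placebo as own control: 21/24 − 20/44 = 87.5% − 45.5% = +42.0 points; χ² = 11.47, p = 0.0007.
- Randomized, one enema: 28/42 − 20/44 = 66.7% − 45.5% = +21.2 points; χ² = 3.92, p = 0.048, which reproduces the protocol's figure.
- With the SAP Table 1 counts: 25/42 − 19/44 = +16.3 points, p = 0.13.

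The protocol reports p below 0.0001 for the own-control contrast, which Pearson's test on these counts does not give. McNemar's test (21 vs 0 discordant) gives about 1×10⁻⁶, and so does 41/44 vs 20/44. The documents do not say which test was used.

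**8. What significance would need here.** At design rates and full uptake, 42/90 requires at least 31/48 (65%, p = 0.045) in 7.6.3.6. In 7.6.3.7, 124/180 requires at least 47/56 (84%, p = 0.028), since 46/56 gives p = 0.054.

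**The case against.** The strongest defence is that these are other endpoints, outside the closed procedure, and no success rule or sample size depends on them. The section titles already say open-label and name the subjects as failures, and 7.6.3.7 already plans the retreatment rate itself. All of that is true, and it keeps the point away from the primary and secondary conclusions. It does not make the p-values interpretable. The SAP does rule out inference where it chooses to, as for the Cdiff32 scores in 7.6.3.2, but not here.

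The second defence is that the bias may run against RBX2660. This also stands. A reader might infer that the test necessarily credits selection and antibiotics to the drug. The documents do not support that. Selection on failure normally lowers retreatment success (step 4), and only selection by election could raise it. Antibiotics were required before the blinded enema and are permitted before the open-label one, so they are a possible imbalance without an established direction.

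A reader might also infer that small p-values are bound to follow. That is not shown, least of all for the second enema. The open-label Phase 2 study reports 78.6% after two treatments (Protocol 1.5.1). As an illustrative rate, 44/56 against 124/180 gives p = 0.16.

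**Conclusion.** The point holds as a limit on interpretation. Both tests compare retreated failures with their entire arm of origin, without a concurrent control, and the result cannot separate RBX2660 from prior failure, election, open-label care, time and antibiotic rules. Because the sign of the bias is unknown, the p-value is uninformative in either direction.

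No single size can be given. Depending on assumed ρ and shift, the rate of false significance favouring retreatment runs from below 1% to 63% (7.6.3.6) or 88% (7.6.3.7).

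The 2014-01 gap of 42.0 against 21.2 points shows that such a contrast can differ from a randomized one. A reader might take the excess as a measure of bias, but the documents do not support that. They do not say how many open-label enemas the 24 subjects received, and Protocol 1.5.2 reports up to four RBX2660 exposures per subject when the blinded phase allowed two. The group is also small: 21/24 against the randomized 28/42 gives p = 0.063. Finally, the placebo count differs between documents (20/44 and 19/44), so a ratio built from both is inconsistent.

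It is worth correcting before unblinding, but it is not a threat to the trial's main claim.

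**What to change.** In SAP 7.6.3.6 and 7.6.3.7, delete the chi-square tests. For each group separately (placebo failures given open-label RBX2660, and RBX2660 failures given a second enema), report:

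- the number eligible and the number who elected retreatment;
- the 8-week success proportion after the open-label enema, with an exact (Clopper-Pearson) 95% confidence interval.

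State that the result is uncontrolled and that subjects were selected by failure and by choice. Give no p-value against the blinded arm. For scale, 21/24 would be reported as 87.5% with an interval of 67.6% to 97.3%, from the 2.5% quantile of Beta(21, 4) and the 97.5% quantile of Beta(22, 3).

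This answers Other Objectives 7 and 8 as far as the design allows. It changes SAP wording only, with no new data and no change to conduct or sample size. The loss is two exploratory p-values.
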